#### 1.2. Trial Design

This is a multicenter, double-blind, randomized, parallel-group, placebo-controlled, 6-week adaptive dose-finding study to assess the efficacy and safety of JNJ-42847922 as adjunctive therapy in adult subjects with MDD who have had an inadequate response to current antidepressant therapy with an SSRI/SNRI. Approximately 280 subjects will be randomized.

The doses of JNJ-42847922 that will be studied prior to the interim analysis are known (i.e., 20 and 40 mg), whereas the doses of JNJ-42847922 to be studied after the interim analysis will be adaptively chosen based on the dose-response curve observed at the interim analysis. During the interim analysis review period, subjects will continue to be randomized according to the initial randomization scheme. Regardless of whether subjects are randomized before or after the interim analysis, the schedule of events and study procedures will remain the same. The final analysis will include all subjects.

Initially, the study will assess the efficacy, dose- and exposure-response relationship, safety, and tolerability of JNJ-42847922 20 and 40 mg doses compared to placebo, when administered as adjunctive therapy to an SSRI/SNRI antidepressant. At the start of the study, subjects will be randomized in a 2:1:1 ratio to receive 1 of 3 treatments: placebo: JNJ-42847922 20 mg: JNJ-42847922 40 mg.

The data cutoff for the interim analysis will be 6 weeks after randomization of 160 subjects. An Interim Analysis Committee (IAC) will be established to review the interim data to examine the dose-response relationship and determine the doses of JNJ-42847922 and the allocation ratio of the doses to be used after the interim analysis.

After the interim analysis, subjects will be randomly assigned to study drug (placebo or 1 of the JNJ-42847922 doses [potential doses include 10 mg, 20 mg, 40 mg]), with the allocation ratio adapted according to the dose-response curve seen at the interim analysis.

For all subjects, the study will consist of 3 phases: a screening phase (up to 4 weeks), a doubleblind treatment phase (6 weeks), and a posttreatment follow-up phase (2 weeks). The planned total study duration for each subject will be approximately 12 weeks (84 days). Subjects will continue to take their baseline SSRI/SNRI antidepressant (at the same dose, without change, and at approximately the same time as prior to entering the study) throughout the screening, doubleblind, and follow-up periods (the entire 12 weeks of the study duration).

In order to collect PK and salivary cortisol samples after the Day 1 dose, subjects will stay at the study site from at least 1 hour before the bedtime dosing on Day 1 until the morning of Day 2.

A schematic overview of the study design is provided in Figure 1.

#### Figure 1: Schematic Overview of the Study Design

**Abbreviations:** IA=interim analysis, MDD=major depressive disorder, PK=pharmacokinetics, QD=once daily, SSRI= selective serotonin reuptake inhibitor, SNRI=serotonin-norepinephrine reuptake inhibitor.

#### **1.3.** Statistical Hypotheses for Trial Objectives

The primary efficacy endpoint is the change from baseline to the end of Week 6 in the MADRS total score. The null hypothesis to be tested to address the primary objective of the study is that there is no difference between any of the JNJ-42847922 doses (10, 20 and/or 40 mg) and placebo, as adjunctive treatment to an SSRI/SNRI, in the improvement of depressive symptoms of MDD, based on the primary efficacy endpoint.

#### 1.4. Sample Size Justification

The calculation of the sample size is based on the primary efficacy endpoint (change from baseline to the end of Week 6 for the MADRS total score). The assumptions for the effect size were based on published literature and the clinically meaningful difference between groups to be detected.

The total sample size is calculated on the basis of the generalized Multiple Comparison Procedure-Modeling (MCP-Mod) test applied to the placebo and the JNJ-42847922 dose groups at the final analysis. Approximately 280 randomized subjects will provide an average weighted power of approximately 85% depending on the underlying true dose-response shape, assuming a 1-sided significance level of 0.05, a treatment difference from placebo of 4.5 points in change in MADRS total score, a standard deviation of 10, and a 25% overall dropout rate.

The data cutoff for the interim analysis will be 6 weeks after randomization of 160 subjects, which corresponds to approximately 57% of the sample size of the study. This number of subjects provides approximately 93% power to detect a dose-response relationship, depending on

the underlying true dose-response shape, assuming a treatment difference of 4.5, and a standard deviation of 10 when tested by means of the MCP-Mod approach at the 30% significance level (1-sided).

Further details regarding the interim analysis will be specified in a separate charter and interim analysis SAP.

#### 1.5. Randomization and Blinding

Central randomization will be implemented in this study. Subjects will be randomly assigned based on a computer-generated randomization schedule prepared before the study by or under the supervision of the sponsor.

At the start of study enrollment, subjects will be randomly assigned to receive 1 of 3 treatments in a 2:1:1 ratio to placebo:JNJ-42847922 20 mg:JNJ-42847922 40 mg.

After the interim analysis, subjects will be randomly assigned to study drug, with the allocation ratio adapted according to the dose-response curve observed at the time of the interim analysis. Subjects will be assigned to receive placebo or one of the JNJ-42847922 doses (potential doses include 10 mg, 20 mg, 40 mg).

The randomization will be balanced by using randomly permuted blocks and will be stratified by region (United States [US], Europe, and Japan) and by insomnia status (significant insomnia symptoms [ISI score  $\geq$ 15] at baseline versus no significant insomnia symptoms [ISI score <15] at baseline). In order to randomize approximately equal proportions of subjects with and without significant insomnia symptoms at baseline, the number randomized in either stratum will be capped at 60% of the planned total sample size.

The interactive web response system (IWRS) will assign a unique treatment code, which will dictate the treatment assignment and matching study drug kit for the subject. The requestor must use his or her own user identification and personal identification number when contacting the IWRS, and will then give the relevant subject details to uniquely identify the subject.

To maintain the study blind, the study drug container will have a label containing the study name, study drug number, and reference number. The label will not identify the study drug in the container. However, if it is necessary for a subject's safety, the study blind may be broken and the identity of the study drug ascertained. The study drugs will be identical in appearance and will be packaged in identical containers.

In general, randomization codes will be disclosed fully only when the study is completed and the clinical database is closed. However, for the interim analysis, the randomization codes and the translation of randomization codes into treatment and control groups will be disclosed to those authorized and only for those subjects included in the interim analysis.

#### 2. GENERAL ANALYSIS DEFINITIONS

#### 2.1. Study Reference Start and End Dates

The overall reference start date for the study is defined as the date of the first dose of doubleblind medication (the date is missing for screened subjects who did not receive a dose of doubleblind medication). The overall reference end date for the study is the end of trial date including the last follow-up visit, i.e., the study reference end date is the maximum of the date of the last visit in the double-blind treatment phase, or date of the last visit in the follow-up phase, or date of disposition in the double-blind phase (Trial Disposition for Double-blind Phase case report form [CRF] page), or date of disposition in the follow-up phase (Disposition at Follow-up CRF page).

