12.3. Procedures

12.3.1. All Adverse Events

All adverse events and special reporting situations, whether serious or non-serious, will be reported from the time a signed and dated ICF is obtained until completion of the subject's last study-related procedure, which may include contact for follow-up of safety. Serious adverse events, including those spontaneously reported to the investigator within 30 days after the last dose of study drug, must be reported using the Serious Adverse Event Form. The sponsor will

evaluate any safety information that is spontaneously reported by an investigator beyond the time frame specified in the protocol.

All events that meet the definition of a serious adverse event will be reported as serious adverse events, regardless of whether they are protocol-specific assessments. Anticipated events will be recorded and reported as described in Attachment 2.

All adverse events, regardless of seriousness, severity, or presumed relationship to study drug, must be recorded using medical terminology in the source document and the CRF. Whenever possible, diagnoses should be given when signs and symptoms are due to a common etiology (eg, cough, runny nose, sneezing, sore throat, and head congestion should be reported as "upper respiratory infection"). Investigators must record in the CRF their opinion concerning the relationship of the adverse event to study therapy. All measures required for adverse event management must be recorded in the source document and reported according to sponsor instructions.

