12.3.2. Serious Adverse Events

All serious adverse events occurring during the study must be reported to the appropriate sponsor contact person by study-site personnel within 24 hours of their knowledge of the event.

Information regarding serious adverse events will be transmitted to the sponsor using the Serious Adverse Event Form, which must be completed and signed by a physician from the study site, and transmitted to the sponsor within 24 hours. The initial and follow-up reports of a serious adverse event should be made by facsimile (fax).

All serious adverse events that have not resolved by the end of the study, or that have not resolved upon discontinuation of the subject's participation in the study, must be followed until any of the following occurs:

- The event resolves
- The event stabilizes
- The event returns to baseline, if a baseline value/status is available
- The event can be attributed to agents other than the study drug or to factors unrelated to study conduct
- It becomes unlikely that any additional information can be obtained (subject or health care practitioner refusal to provide additional information, lost to follow-up after demonstration of due diligence with follow-up efforts)

Suspected transmission of an infectious agent by a medicinal product will be reported as a serious adverse event. Any event requiring hospitalization (or prolongation of hospitalization) that occurs during the course of a subject's participation in a study must be reported as a serious adverse event, except hospitalizations for the following:

- Hospitalizations not intended to treat an acute illness or adverse event (eg, social reasons such as pending placement in long-term care facility).
- Surgery or procedure planned before entry into the study (must be documented in the CRF). Note: Hospitalizations that were planned before the signing of the ICF, and where the underlying condition for which the hospitalization was planned has not worsened, will not be considered serious adverse events. Any adverse event that results in a prolongation of the originally planned hospitalization is to be reported as a new serious adverse event.

The cause of death of a subject in a study within 30 days of the last dose of study drug, whether or not the event is expected or associated with the study drug, is considered a serious adverse event.

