#### **Double-blind Phase**

The analysis reference start date of the double-blind analysis phase is the date of the first dose of double-blind medication. The analysis reference end date of the double-blind analysis phase (except for Adverse Events) is the maximum of the date of the last visit in the double-blind phase and date of completion or early withdrawal from the double-blind phase (Trial Disposition for Double-blind Phase CRF page). For Adverse Events, the analysis reference end date of the double-blind analysis phase is the date of the last dose of study drug plus 2 days. For randomized subjects who did not receive any medication in the double-blind phase, both analysis reference start and end dates are missing for the double-blind analysis phase.

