#### 6.1. Adverse Events

The verbatim terms used in the CRF by investigators to identify AEs will be coded using the Medical Dictionary for Regulatory Activities (MedDRA). Any AE occurring at or after the initial administration of study drug through the day of last dose plus 2 days is considered to be treatment-emergent. If the AE occurs on the day of the initial administration of study drug, and either the AE time or time of administration are missing, then the AE will be assumed to be treatment-emergent. If the AE date is recorded as partial or completely missing, then the AE will be considered to be treatment-emergent unless it is known to be prior to the first administration of study drug based on partial onset date or resolution date.

All reported treatment-emergent adverse events (TEAEs) will be included in the analysis. For each TEAE, the number and percentage of subjects who experience at least 1 occurrence of the given event will be summarized by system organ class, preferred term, and treatment group.

Summary tables will be provided for:

- TEAEs
- TEAEs occurring in  $\geq$ 5% of subjects in any treatment group
- Treatment-emergent serious AEs (SAEs)
- TEAEs leading to discontinuation of study drug
- TEAEs by severity
- TEAEs by relationship to study drug

For the summaries of TEAEs by severity/relationship to study drug, the observation with the most severe occurrence/closest relationship to study drug will be chosen if there is more than one incident of the same TEAE for the subject.

In addition, a summary table will be generated showing the number and percentage of subjects who experience at least 1 occurrence of a given TEAE by system organ class, preferred term, lowest level term, and treatment group.

A summary of all somnolence-related TEAEs (MedDRA preferred terms: somnolence, hypersomnia, and sedation; regardless of start time) will be presented.

Adverse events of special interest are cataplexy, sleep paralysis, and complex, sleep-related behaviors (parasomnias). Subjects with TEAEs of special interest will be presented separately, by preferred term and treatment group. The AEs to be included in the summary of TEAEs of special interest are marked as such on the AE CRF.

A summary table of non-TEAEs occurring on or after the date of last dose of study drug plus 3 days until the overall reference end date for the study will also be provided.

In addition to the summary tables, listings will be provided for subjects who:

- Died

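### SAEs and deaths that begin after a subject's last visit or disposition date, but within 30 days of the last dose, enter no planned summary table and appear only in listings

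*SAP*

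**What the plan says.** Four rules set where a post-dose event is counted.

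- **On-treatment window.** For adverse events, SAP 2.2 (Double-blind Phase) states that the "end date of the double-blind analysis phase is the date of the last dose of study drug plus 2 days". SAP 6.1 agrees: an event "through the day of last dose plus 2 days is considered to be treatment-emergent". The only SAE table on the SAP 6.1 list is restricted to treatment-emergent events.
- **Post-treatment window.** SAP 6.1 plans one summary of non-TEAEs, those "on or after the date of last dose of study drug plus 3 days until the overall reference end date for the study". It does not say that this table is split by treatment group or by seriousness.
- **Reference end date.** SAP 2.1: "The overall reference end date for the study is the end of trial date including the last follow-up visit". In practice this is the latest of the last double-blind visit, the last follow-up visit and the two disposition dates. It has no extension for adverse events.
- **Protocol reporting period.** Protocol 12.3.1 collects all adverse events up to the last study-related procedure, then goes further for serious ones: "Serious adverse events, including those spontaneously reported to the investigator within 30 days after the last dose of study drug, must be reported". Protocol 12.3.2 makes an SAE of "The cause of death of a subject in a study within 30 days of the last dose of study drug".

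SAP 6.1 also plans by-subject listings of deaths and of SAEs, with no time limit and no restriction to treatment-emergent events.

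**The concern.** The SAP carries over the protocol's period for routine adverse events but not its longer period for serious ones. An SAE or death that begins after the reference end date and by day 30 is too late for the treatment-emergent tables and for the non-TEAE table.

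Safety and tolerability against placebo is a primary objective, and Protocol Attachment 2 names suicidal thinking and behavior as anticipated events in this population. A listing records such an event but gives no count by arm with a denominator. A second weakness applies to every subject: because the non-TEAE table is not specified by arm or by seriousness, and deaths have only a listing, the SAP specifies no by-arm SAE count beyond last dose plus 2 days.

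**Working it through.** This is day arithmetic; no power or sample-size figure bears on it.

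**Inputs**
- Last planned dose: Day 41 (Protocol Section 6).
- Follow-up visit: 7 to 14 days after Day 42 (Protocol 9.1.4), given as Days 49-56 in Protocol 10.1.
- Visit window: ±2 days (Time and Events Schedule).
- Treatment-emergent cut: last dose + 2. Non-TEAE table: last dose + 3 to reference end date R (SAP 6.1).
- SAE and death limit: last dose + 30 (Protocol 12.3.1, 12.3.2).

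**Reproducing the plan's own figures.** 42 + 7 = 49 and 42 + 14 = 56, which matches Days 49-56. 28 + 42 + 14 = 84 days, which matches the stated study duration per subject.

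**Completer**
- Treatment-emergent tables end on Day 41 + 2 = 43, covering 2 post-dose days.
- The non-TEAE table runs from Day 44 to R, which is R − 43 days.
- The 30-day limit is Day 41 + 30 = 71.
- Days in no summary table = 71 − R.

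| R (last visit) | TEAE days | Non-TEAE days | Days in no table | Share of 30 |
|---|---|---|---|---|
| Day 49 | 2 | 6 | 22 (Days 50-71) | 73% |
| Day 56 | 2 | 13 | 15 (Days 57-71) | 50% |
| Day 47 (49 − 2) | 2 | 4 | 24 (Days 48-71) | 80% |
| Day 58 (56 + 2) | 2 | 15 | 13 (Days 59-71) | 43% |

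Each row sums to 30. The last two rows assume that the ±2-day window applies on top of Days 49-56.

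**Subject with no follow-up visit and R no later than last dose + 2.** The non-TEAE window is empty, so days +3 to +30 are in no table: 30 − 2 = 28 days, or 93%. This is the extreme case. The sample-size section assumes 25% dropout (0.25 × 280 = 70 subjects), but the documents do not say how many of those would also miss follow-up.

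**Number of events.** The documents give no expected SAE rate. Assume a constant rate r of 1% to 5% per 84 days in 280 subjects, and a gap of g days for each. Expected untabulated SAEs = 280 × r × g / 84.
- Low: 280 × 0.01 × 15 / 84 = 0.5.
- High: 280 × 0.05 × 22 / 84 = 3.7.

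These are totals over all arms and assume that every such event is reported.

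**The case against.** A reader might infer that all SAEs and deaths in the 30 days after the last dose fall outside the tables, or that SAP 2.1 alone closes the adverse event period. The documents do not support either reading. For a completer, 8 to 15 of the 30 days are tabulated: 2 in the treatment-emergent tables and 6 to 13 in the non-TEAE table. SAP 2.1 is a general date definition that acts only through SAP 6.1, and the SAE table is cut by the separate rule of last dose plus 2 days. The SAP also places events by onset, so an on-treatment SAE that is reported late is still treatment-emergent.

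Nor is there a breach of the protocol. Protocol 11.7 promises percentages by treatment group only for treatment-emergent events. For deaths and SAEs it leaves open whether summaries, listings or narratives are given.

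The strongest defense is that the late window is passive. The 30-day clause concerns spontaneous reports, and no contact is scheduled after the follow-up visit. Ending the tables where active collection ends is defensible, and individual listings suit rare events. The 28-day case is also a worst case: Protocol 10.2 asks early leavers to attend end-of-treatment and follow-up assessments, and a death during follow-up may fall inside the period if the disposition page carries its date, which the documents do not state. Protocol 1.1.2 reports no deaths or SAEs in subjects dosed so far (271 subjects), and a mean half-life of 2 to 3 hours, so 48 hours already spans at least 48 / 3 = 16 half-lives.

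Most of this stands and limits the size of the point. It does not close the gap. Passive reporting under blinding loses events but should not favor an arm. The half-life does not settle relevance, because Protocol Section 1 reports an antidepressant effect lasting at least 14 days after treatment stopped.

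**Conclusion.** A narrow gap of low severity is confirmed. No planned summary table holds an SAE or death with onset after the overall reference end date and within 30 days of the last dose. For a completer the gap is 15 to 22 of 30 days, or 13 to 24 with the visit window. It reaches 28 days only with no follow-up visit and a disposition date by last dose plus 2.

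The completer figures rest on a last dose on Day 41 and on the follow-up visit being the latest of the four dates in SAP 2.1; a later disposition date would shorten the gap. The event count of roughly 0.5 to 4 rests wholly on an assumed SAE rate.

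A reader might conclude that late serious events would go unreported. That is not so: every one is listed by subject. What is missing is a prespecified comparison between arms over the period in which the protocol asks for serious events to be reported.

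**What to change.** Change SAP 6.1 only. Leave SAP 2.1, the treatment-emergent definitions and all existing tables as they are. Add one table for the safety analysis set, by treatment group, giving the number and percentage of subjects with an SAE and the number who died, with onset from first dose to the later of the overall reference end date and last dose plus 30 days.

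Footnote the table to say that after the follow-up visit only SAEs are captured, through spontaneous reports.

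The cost is one short SAP paragraph and one table, from data already collected under Protocol 12.3. The downside is incomplete ascertainment in the last part of the window, which the footnote discloses. Because the non-TEAE table is not extended, it does not mix actively collected and spontaneously reported events.

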#### 2.2. Analysis Phases

There are 3 analysis phases defined in this study: Screening, Double-blind, and Follow-up (post double-blind). Each analysis phase has its own analysis reference start date.

#### Screening

The screening phase begins on the date informed consent is obtained and ends 1 day prior to the date of the first dose of study drug in the double-blind treatment phase. The screening phase end date is left missing for those subjects who did not receive study drug.

